8.7 Treatment Application

Subjects will receive a kit containing study drug for application throughout the study. Subjects will be instructed in the use of the spray bottle and asked to self-administer the Investigational Product as follows:

- Subjects will apply a total of 8 pumps of IP per application to all affected areas twice-a-day (i.e. 8 pumps in the morning and 8 pumps again at night).
- Subject should saturate the application area well.
- Subjects may not wash the application site after applying the IP

- Subjects will be asked to let the product air dry.
- While in use, one spray bottle may be stored at ambient temperature. The bottle that is not in current use by the subject, must be stored in the refrigerator. DO NOT FREEZE.

8.8 Treatment of Investigational Product Overdose

The sponsor does not recommend specific treatment for an overdose. Washing with conventional cleanser and water will remove the product. The Investigator will use clinical judgment to treat any overdose.

8.9 Product Accountability

In accordance with federal and local regulatory requirements, the Investigator and designated site personnel must document the amount of investigational product dispensed to study participants, the amount returned by study participants, and amount received and returned to the sponsor, when applicable. Product accountability records must be maintained throughout the course of the trial. Any quality issue noticed with the receipt or use of an IP (deficient IP in condition, appearance, pertaining documentation, labeling, expiry date, etc.) should be promptly reported to the Sponsor, who will initiate a complaint procedure.

All investigational product must be stored in a secure locked room with access limited to the Investigator and designated site personnel. Study product is to be stored in a refrigerator between 2-8 degrees C. Maintenance of a temperature log is required.

Under no circumstances will the Investigator allow IP to be used other than as directed by this Clinical Trial Protocol, or dispose of IP in any other manner.

8.10 Unblinding Procedures

The Investigator may unblind a participant's treatment assignment only in the case of emergency or in the event of a serious medical condition when knowledge of the study treatment is essential for the appropriate clinical management or welfare of the participant, as determined by the Investigator. It is preferred (but not required) that the Investigator first contacts the medical monitor to discuss options before unblinding the participant's treatment assignment. The Investigator must notify the Sponsor as soon as possible when a participant's treatment assignment is unblinded without revealing the treatment assignment of the unblinded participant unless that information is deemed important for the safety of participants currently in the study. The date and reason for the unblinding must be documented in the participant's study record.

The Medical Monitor may unblind the treatment assignment for any participant with an SAE. If the SAE requires that an expedited regulatory report be sent to one or more regulatory agencies, a copy of the report, identifying the participant's treatment assignment, may be sent to clinical Investigators in accordance with local regulations and/or sponsor policy.

8.11 Retrieval and Destruction of Investigational Product

All partially used or unused treatments will be returned to the site as brought by study participants. A detailed IP log of the returned IP shall be established.

The site will not destroy unused IP unless the Sponsor provides written authorization to the contrary. All used and unused bottles will be shipped to the authorized drug depot at the end of the study.

8.12 Permitted Medications

All participants will be screened for concomitant medications prior to inclusion into the study. Any concomitant medication to treat adverse events will be recorded in the Concomitant Medication section of the eCRF.

8.13 Prohibited Medications

Participants will be prohibited from taking any of the following therapy, including topical corticosteroids, oral/IV/inhaled steroids, topical coal tar, topical sulfur, topical PDE-4 inhibitors, topical or oral antihistamines, topical antiseptics or antibiotics, topical antifungals, bleach baths, UVA or UVB phototherapy, oral antibiotics/antiviral/antifungal/antiseptic agents, systemic immunosuppressive or immunomodulatory agents, oral or topical probiotics for the duration of the trial.

8.14 Rescue Medications

Rescue medications will not be permissible in the trial should the study subject experience acute exacerbation of symptoms related to the treated disease. Subject may not start additional non-randomized medication and should immediately alert the study site PI. Subjects that need to start a rescue medication will be discontinued from the study and will be considered an Early Termination.

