7.3 Study Withdrawal and Withdrawal From Investigational Product and Stopping Criteria

A participant may withdraw from the study at any time at his/her own request, or may be withdrawn at any time at the discretion of the Investigator.

Reasons for withdrawal (participants who refuse to complete any remaining study visits) or discontinuation (participants who prematurely stop the application) at any time during the study may include, but are not limited, to the following:

- For safety reasons, either at the discretion of the Investigator or at the participant's request
- For protocol violations at the discretion of AOBiome
- Due to concomitant therapy that could interfere with the results of the study (the Investigator will report all such information on the CRFs and decide, in accordance with AOBiome, whether the participant is to be withdrawn).

The reason for participant study withdrawal will be recorded in the electronic Case Report Form (eCRF). Data from participants withdrawing from the study will be considered evaluable up to the point at which they are withdrawn using the same criteria for evaluability as for participants who complete the study.

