13.4 Subject Withdrawal Criteria

A subject may withdraw from the study at any time at his/her own request, or may be withdrawn at any time at the discretion of the Investigator for safety, behavioral, or administrative reasons.

Reasons for withdrawal (subjects who refuse to return for any remaining study visits) or discontinuation (subjects who prematurely stop the application) at any time during the study may include, but are not limited, to the following:

- For safety reasons, either at the discretion of the Investigator or at the subject's request
- For protocol violations at the discretion of AOBiome
- Due to concomitant therapy that could interfere with the results of the study (the Investigator will report all such information on the CRFs and decide, in accordance with AOBiome, whether the subject is to be withdrawn).

All premature discontinuations and their causes must be carefully documented by the Investigator on the CRF or if needed on the AE form.

If, for any reason, a subject is withdrawn before completing the final visit, the reason for termination will be entered on the CRF. All data gathered on the subject prior to termination will be made available to AOBiome. Subjects not completing the entire study should be fully evaluated when possible. The appropriate CRFs should be completed.

If the subject chooses to withdraw before completing the study, the subject should notify the study coordinator who will instruct the subject on completion of assessments for End of Study (EOS) visit Appendix A. For

subjects who refuse to complete the assessments for their early termination, every attempt must be made to check on their status, using any mode of communication such as telephone, email, fax, or text.

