16.3 Time Period, Frequency, and Method of Detecting AEs and SAEs

All AEs occurring after administration of the first dose of study medication and on or before the final assessment must be reported as AEs. All AEs must be recorded irrespective of whether they are considered drug-related.

At each assessment in the period defined above, AEs will be evaluated by the Investigator and recorded. Any AEs already documented at a previous assessment and designated as ongoing, should be reviewed at subsequent assessments as necessary. If these have resolved, this should be documented. Changes in intensity or frequency of AEs should be recorded as separate events (i.e., a new record started). The recording of AEs and SAEs are described in Section 164 ("Recording of AEs and SAEs").

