#### 4 5 2 Adverse Events

Adverse events will be analyzed in terms of treatment-emergent adverse events (TEAEs) which are defined as any AEs that begin or worsen on or after the start of study drug through 28 days after the last dose of study drug.

A treatment-related TEAE is defined as a TEAE that was considered by the Investigator to be at least possibly related to the study drugs.

If a subject experiences the same AE more than once with different toxicity grades, the event with the highest grade will be tabulated in the "by grade" tables. If a subject experiences multiple AEs under the same preferred term (SOC), the subject will be counted only once for that preferred term (SOC). In addition, AEs with a missing severity will be presented in the summary table as an intensity category of "Missing."

An overall summary table presenting the number of subjects who experienced the following will be presented by treatment arm: any TEAE, any related TEAE, any Grade 3 or 4 TEAE, any related Grade 3 or 4 TEAE, any serious TEAE, any serious related TEAE, any TEAE leading to discontinuation of treatment, any TEAE leading to study discontinuation, and any TEAE leading to death.

The incidence of TEAEs will be summarized by MedDRA SOC and preferred term. Tables summarizing the incidence of TEAEs will be generated for each of the following:

- x All TEAEs
- **X** TEAEs reported as treatment-related
- x Severe or Grade 3/4 TEAEs
- x Related Grade 3/4 TEAEs
- **▼** Serious TEAEs
- Related Serious TEAEs

If no subjects experience any of the events in the overall summary table, the corresponding table by SOC and preferred term will not be produced.

No formal hypothesis-testing analysis of AE incidence rates will be performed.

All AEs occurring on-study will be listed in subject data listings.

By-subject listings also will be provided for the following: subject deaths, serious AEs, and AEs leading to withdrawal.

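### Protocol 8.14 ends study participation when rescue is needed, 7.3 and 13.4 leave withdrawal for interfering therapy to judgement, and safety and score collection after exit is not settled

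*Protocol*

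**What the plan says.** **Leaving the study.** Protocol 8.14 does not allow rescue medication for an acute flare and adds: "Subjects that need to start a rescue medication will be discontinued from the study and will be considered an Early Termination". The wording is mandatory, and it concerns the study as well as the product.

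Protocol 7.3 and 13.4 use two terms. Withdrawal means refusing the remaining visits. The other term, in 13.4, is "discontinuation (subjects who prematurely stop the application"). For concomitant therapy that could disturb the results, 7.3 has the Investigator "decide, in accordance with AOBiome, whether the participant is to be withdrawn", and 13.4 says the same. Protocol violations are treated separately: "For protocol violations at the discretion of AOBiome". Neither section mentions rescue or treatment of AD.

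Two further sections bear on the same event. Section 8.12 records medication given for adverse events and attaches no withdrawal rule. Section 16.1 counts worsening of a pre-existing condition as an adverse event.

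**After leaving.** Section 11.6.7 gives one Early Termination visit. Section 7.5 then follows only ongoing events thought possibly related to product, until resolution or for 30 days. Section 16.4 follows possibly related events until they resolve. Section 16.7 adds outcome follow-up of adverse events and reporting of later serious events judged related. Section 16.3 limits reporting to events "on or before the final assessment must be reported as AEs".

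**What the analysis expects.** Protocol 15.4.2 and SAP 4.5.2 count events "through 28 days after the last dose of study drug". The synopsis says all subjects are asked to come back 14 (±3) days after the last dose and are followed to Day 42. The primary objective is safety and tolerability. Missing data are not imputed (Protocol 15.4.6; SAP 3.10).

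**The concern.** A topical corticosteroid started for a flare is prohibited under 8.13, is rescue under 8.14, and is interfering therapy under 7.3 and 13.4. If it is given because the flare was recorded as an adverse event, 8.12 applies as well. Sites could therefore handle the same event differently: one subject leaves, while another stays and contributes scores taken after the steroid.

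The subjects concerned are those who get worse, so what is lost is not a random sample. Later adverse event terms are missed in the people most informative about tolerability. Their Day 28 and Day 42 EASI, IGA and VAS scores are lost too: SAP 4.3.1 summarises only Baseline and Days 14, 28 and 42, SAP 3.11 tabulates by the visit named on the CRF, and the SAP gives Early Termination scores no place. If such exits differ between arms, the arms are observed for different lengths of time. The adverse event tables show simple percentages of the Safety population, with no adjustment for time observed.

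**Working it through.** **Planned dropout.** The inputs are in Protocol 15.1: 52 per group, difference 3.9, SD 7.0, one-sided alpha 0.025, 130 randomized, 20% dropout.

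- Noncentrality = 3.9 / (7.0 × √(2/52)) = 2.84. With 102 degrees of freedom, exact t-test power is 0.803, so the stated power above 80% reproduces.
- 104 / (1 − 0.20) = 130, so planned dropouts are 130 − 104 = 26.

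These 26 are dropouts for any reason. The documents do not say how many would be rescue exits.

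**Observation per subject.** Scheduled follow-up runs to Day 42 and the analysis window to 28 days after the last dose. Days lost = 42 − exit day. Window days that fall before Day 42 = the smaller of 28 and (42 − last-dose day).

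| Last dose and exit | Days lost to Day 42 | Analysis window ends | Window days before Day 42 |
|---|---|---|---|
| Day 7 | 35 | Day 35 | 28 |
| Day 14 | 28 | Day 42 | 28 |
| Day 21 | 21 | Day 49 | 21 |
| Day 28 | 14 | Day 56 | 14 |

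If the Early Termination visit falls on the day of the last dose and is the last contact, none of the 28-day window has a scheduled contact. A completer has 14 of the 28 days covered. Attending through Day 42 would cover the whole window for anyone who stops by Day 14.

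**Observation across the trial.** Planned total = 130 × 42 = 5,460 subject-days. Loss = 26 × rescue share × (42 − mean exit day). With a mean exit at Day 14 (assumption):

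- 25% of dropouts: 6.5 × 28 = 182; 182 / 5,460 = 3.3%.
- 50%: 13 × 28 = 364; 364 / 5,460 = 6.7%.
- 100%: 26 × 28 = 728; 728 / 5,460 = 13.3%.

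The exit day matters as well. With all 26 as rescue exits, a mean exit at Day 7 gives 26 × 35 / 5,460 = 16.7%, and at Day 21 gives 26 × 21 / 5,460 = 10.0%.

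**Follow-up rules side by side.** For a subject whose last dose is on Day 14, 11.6.7 provides one Early Termination visit. The first synopsis statement gives a visit at Day 14 + 14 = Day 28 (±3), and the second gives follow-up to Day 42. The two synopsis statements agree for a completer (28 + 14 = 42) but not for an early stopper. The analysis window runs to Day 42. No section puts these in order.

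**The case against.** The best counter-argument is that 8.14 is the specific rule for flares of the treated disease, while 7.3 and 13.4 are open lists of reasons covering any concomitant therapy. On that reading the specific rule governs and nothing conflicts. The reading is fair, which is why a flat contradiction should not be claimed. But no text states it, so the ambiguity stands.

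A reader might infer several stronger points that the documents do not support:

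- *The sponsor alone decides who stays.* For interfering therapy the Investigator decides, in accordance with the sponsor. Sole sponsor discretion is stated only for protocol violations.
- *Safety follow-up ends at exit.* The Early Termination visit includes adverse events, examination, vital signs and scores, with laboratory tests if before Week 4. Sections 7.5, 16.4 and 16.7 keep some follow-up, and 13.4 wants non-completers fully evaluated where possible. The gap is new non-serious events.
- *The Early Termination visit is the final assessment of 16.3.* That term is not defined, and 13.3 makes Day 42 the last visit.
- *The overall adverse event percentage is badly biased.* A flare that leads to exit would normally be recorded as an adverse event, so the subject already counts in the row for at least one event. The effect falls on later, different terms.
- *Scores after a steroid count without limit.* Prohibited medication is a named deviation that can exclude a subject from the per-protocol population before unblinding (SAP 2.2). The point applies to ITT.
- *Staff who can see the product choose between the rules.* Section 8.1 describes liquids of different appearance, but in identical white bottles. Nothing links this to withdrawal decisions.

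**Conclusion.** The concern holds as an unresolved ambiguity with a real gap in data collection. The plan does not say whether 8.14 or the judgement in 7.3 and 13.4 governs AD treatment. It also does not say how new non-serious adverse events are to be collected between exit and the end of the analysis window. The synopsis visit for all subjects would partly close that gap, but 11.6.7 does not carry it through.

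The size is unknown because the rescue share is not given. About 3% to 13% of scheduled observation days would be lost, assuming that 25% to 100% of the 26 planned dropouts are rescue exits at a mean of Day 14. The upper figure treats every dropout as a rescue exit and is not an estimate. Because the loss falls on subjects who worsen, its selectivity matters more than its volume. The documents give no basis for a direction or size of bias between arms.

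**What to change.** Reconcile the synopsis (assessment schedule and duration) with Protocol 7.3, 7.5, 8.14, 11.6.7, 13.4, 15.4.2 and 16.3, so that one reading applies to AD treatment and to follow-up after exit, and define the final assessment in 16.3. This review takes no position on whether rescue should be allowed or when product should be stopped.

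For data collection only:

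1. State that subjects who stop product are asked to attend the remaining scheduled Day 14, 28 and 42 visits for adverse events, laboratory tests and EASI, IGA and VAS.
2. Keep the Early Termination visit for those who decline.
3. Flag scores taken after new AD treatment, and state in the SAP how flagged scores are handled, identically in both arms.

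The cost is amendment wording, a data flag, a short SAP paragraph, and the visits themselves for subjects who would otherwise have left. Those visits are already in the schedule; the documents give no budget. The downsides are that some retained scores will reflect the new treatment, hence the flag, and that subjects who refuse visits are not recovered.

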8.15 Lifestyle Restrictions

8.15.1 Use of cleanser and moisturizer during the trial

At the beginning of the trial, subjects will be provided cleanser and moisturizer to use for the duration of the trial as needed. Subjects will be asked not to use any other cleansers, or moisturizers during the course of active treatment. (Baseline-Day 28). Although moisturizer is provided to subjects, its use it not mandatory in the study and may be used when and as needed only. If subjects do not have the need to use the moisturizer, they may forego its use all together.

Although study cleanser is provided, subjects will be asked to refrain from washing the treatment areas with study cleanser starting from Washout through Day 28. Subjects may use cleanser to wash other parts of their body not treated during the study. At Day 28 (end of study drug application) subjects will be asked to return cleanser that were provided to them by the sponsor and will be asked to go back to their regular regimen and use their preferred cleanser.

Provided moisturizer may be applied to the application site AFTER IP administration. Subject should apply the IP as instructed, let the site of application dry and only then apply the moisturizer.

Subjects may not wash application area with cleanser and water AFTER each application.

8.16 Handling of Investigational Product

Subjects will receive a kit containing two 30 ml white bottles. Each bottle will be used for one week and brought to all study appointments (Day 14, Day 28, Unanticipated visit, EOS visit). Subjects will be asked to refrigerate bottles that are not in use. The bottle which is being used for treatment at a given week may be placed on the counter to be used during the treatment period.

Subjects will be asked not to subject the treatment kit to conditions which are unnatural or harmful to the product, such as excessive heat (temperatures over 77°F (25°C) and freezing temperatures (at 0°C). Subjects may travel with their study medication but should not leave it in the hot car, outside in the cold temperatures etc. Subjects will also be asked not to tamper or cause damage to IP.

8.17 Treatment compliance

Each site participating in the trial will be instructed to assess subject's compliance by weighing the investigational product and obtaining the weight of the bottle in grams pre and post application (after two weeks of use). Study personnel will be asked to take out bottles from the carton, weigh both bottle and record the weight. At the Day 14 visit, study personnel will need to weigh both bottles without the carton and record weight. This procedure should be followed every time study medication is dispensed and returned. Sites will be provided scales, which will be calibrated prior to each use. Study personnel will be instructed to record measurements into the eCRF.

9 ACTIGRAPHY WATCH

At Baseline visit, subjects will be provided two actigraphy watches in order to accurately monitor subject's sleep, activity and itching patterns. Subjects will be asked to wear one watch on each wrist 24 hours a day starting with the Baseline visit through Week 4 visit. Actigraphy watches are water resistant and may be left on when bathing/showering/swimming. However, for convenience, subjects may remove watches during the above mentioned procedures but will be asked to put watches back on once these procedures have been completed.

Any deviations will be recorded in the CRF.

10 CONTRACEPTION REQUIREMENTS

Effective contraception is required for all women physiologically capable of becoming pregnant during study participation. Women of child-bearing potential must agree to use an acceptable form of contraception for up to 2 weeks after the study completion as detailed. Women of childbearing potential are defined as any female who has experienced menarche and who is NOT permanently sterile or postmenopausal. Postmenopausal is defined as 12 consecutive months with no menses without an alternative medical cause.

Effective contraception methods include:

• Total abstinence (when this is in line with the preferred and usual lifestyle of the study participant). Periodic abstinence (i.e., calendar, ovulation, symptothermal, postovulation methods) and

withdrawal are not acceptable methods of contraception.

- Use of oral, injected or implanted hormonal methods of contraception or placement of an IUD or IUS or other forms of hormonal contraception that have comparable efficacy, for example hormone vaginal ring or transdermal hormone contraception.
- Use of barrier methods (i.e., condom, diaphragm) used with a spermicide (i.e., foam, cream, or gel that kills sperm)

In case of use of oral contraception women should have been stable on the same pill for a minimum of 90 days before the baseline visit.

Male participants of the study who are having sexual intercourse with a woman who can become pregnant must use an acceptable form of birth control while participating in the study. Additionally, male participants are expected to let their female partners know of their participation in a research study of a drug, and that the effects of the drug on an unborn baby and on a pregnant woman are unknown. Male participants will also be expected to provide their female partners with the contraception requirements information previously described and the study doctor's contact information for questions.

Payment for all aspects of obstetrical care, child-or related care will be the study participant's responsibility. In case of pregnancy, Investigational Product should be discontinued and the Sponsor should be informed immediately. Follow-up of the pregnancy will be mandatory until the outcome is available.

